8.2.2.2 Hot Flash Daily Diary (HFDD)

Participants' assessments of HF will be recorded electronically twice daily using the Sponsor developed HFDD. The HFDD will be completed in the morning after waking up (morning diary) and each evening at bedtime (evening diary) on the handheld device from visit SCR-1 until EoT as reflected in the SoA. The HFDD items assess the number of mild, moderate, and severe HF experienced during the day and during the night and the severity of sleep disturbances due to HFs experienced during the night.

Mild HF are defined as a "sensation of heat without sweating", moderate HF are defined as a "sensation of heat with sweating, but able to continue activity", and severe HF are defined as a "sensation of heat with sweating, causing cessation (stopping) of activity".

8.2.2.3 Patient-reported Outcomes Measurement Information System Sleep Disturbance Short Form 8b (PROMIS SF 8b)

The PROMIS SD SF 8b includes 8 items assessing sleep disturbance over the past 7 days (Yu et al. 2011). Items assess sleep quality, sleep depth and restoration associated with sleep, perceived difficulties with getting to sleep or staying asleep and perceptions of the adequacy of and satisfaction with sleep. Participants respond to the items on a 5-point scale from not at all, never or very poor to very much, always or very good. Four of the items are scored reversely. Total scores range from 8 to 40, with higher scores indicating greater severity of sleep disturbance. The individual items for a respondent can be summed and raw scores can be converted into T-scores for comparison with population norms.

In this study the PROMIS SD SF 8b will be applied electronically and responded to by the participants at home and during selected in person visits using the handheld device at the time points indicated in the SoA.

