Stratification factor: The stratification factor average weekly frequency of moderate to severe HFs (including nighttime HFs) (see Section 1.2) will be assigned in the IRT system during randomization. The average weekly frequency of moderate to severe HFs is based on HFDD data and will be calculated using the 14 days prior to the visit confirmation date for HF eligibility check. A minimum of 11 days should be available for the calculation of the average weekly value. In case participants are incorrectly stratified, the actual stratification will be used in the analysis. The actual average weekly frequency of moderate to severe HFs will be the value calculated in the eDiary/electronic handheld device. If more than 10% of

Version 2.0 Page: 18 of 57

participants are incorrectly stratified, a sensitivity analysis may be performed using the assigned strata.

Study day 1: Defined as the day of start of treatment, or randomization day if participant did not take study treatment.

Study day: Study day will be calculated using study day 1 as the reference starting day. For observations on or after study day 1, the below formulae will be used:

Study day = date of observation – date of study day 1 + 1

For observations before study day 1, the formulae below will be used:

Study day = date of observation - date of study day 1

Study week: Study week will be calculated for study day >0 using the below formulae:

CEIL is a function in SAS that round up the value to the nearest integer. The calculation would follow the schedule of activities in the protocol (see Section 1.3 in protocol) where day 29 and day 85 with a plus 7-day visit window are specified for week 4 and 12 respectively. This would therefore calculate study day 1 to 7 as study week 0.

Time to event: The start date of treatment for treated participants or the randomization date for randomized participants who did not take study treatment will be used as the start date for the calculation of time to event. Therefore, the time of event will be defined as "date of event – start of treatment date (for treated participants) / randomization date (for randomized but not treated participants) +1".

Unscheduled assessments: Extra assessments (e.g., laboratory data or vital signs) associated with non-protocol visits will be included in listings, but not in the summary tables, unless otherwise specified.

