For the analysis, weekly mean values will be used. The mean daily value for each study week will be calculated by using available data during that week as:

For a particular parameter:

total value of the parameter during that week

total number of available days with morning data for that parameter during that week

Study week will be assigned using the definition in Section 4.1.2 using diary day as the date of observation. Data entered on the morning after the start date of treatment / randomization date will not be used in the calculation of baseline value but will be considered post-baseline.

The mean daily value can be derived if a value is provided for at least 4 out of 7 days with morning data, otherwise the value will be set as missing. The baseline value will be calculated similarly using all available days with morning data during the 14 days prior to starting treatment. A minimum of 7 days should be available for the derivation of the baseline value. Only diary days outside of the impact duration of prohibited hormonal therapies and medication potentially confounding efficacy will be included in baseline derivation. Details regarding the prohibited medications together with the impact duration are described in Section 6.3.

The mean daily value and change from baseline in mean daily value for each parameter will be analyzed using descriptive statistics by study treatment and week. The change from baseline over time by study treatment will be shown using line plots for means and 95% CI.

In addition, the mean daily value from the PSG nights will be summarized descriptively by study treatment and week. The mean value will be calculated using the same rule to calculate the primary endpoint (Section 4.2.1), i.e., if there are sleep diary data for both PSG nights, the mean value of the 2 nights will be used; if only 1 night is available, data from that one night will be used.

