A minimum of 4 days should be available within a study week for the derivation of mean daily frequency, otherwise it will be set to missing for that week. The baseline value will be calculated similarly using all available days with data during the 14 days prior to starting treatment. A minimum of 7 days should be available for the derivation of the baseline value. Only diary days outside of the impact duration of prohibited hormonal therapies and medication potentially confounding efficacy will be included in baseline derivation. Details regarding the prohibited medications together with the impact duration are described in Section 6.3.

A day would be considered as available if morning entry (of the subsequent day) is available when only morning diary is used, or if either evening entry or morning entry (of the subsequent day) is available when both evening and morning diaries are used.

The relationship between the frequency of HFs and WASO as measured by PSG will be explored. The PSG value as defined in Section 4.2.1 will be used in the analysis. Scatterplots showing the below will be produced separately for the actual values, change from baseline and percent change from baseline:

- mean daily frequency of moderate to severe nighttime HFs against WASO as measured by PSG
- mean daily frequency of mild, moderate and severe nighttime HFs against WASO as measured by PSG

Version 2.0 Page: 32 of 57

- mean daily frequency of moderate to severe HFs against WASO as measured by PSG
- mean daily frequency of mild, moderate and severe HFs against WASO as measured by PSG

The mean daily HFs for the same week the week 4 and week 12/EoT PSG assessments fall in will be plotted against each other. Scatterplots will be produced combining all visits on the same plot. In addition, the number of observations and Spearman's rank correlation coefficient and Pearson correlation coefficient with corresponding 95% CI will be computed and presented on the scatterplot.

The mean daily frequency of moderate to severe HFs (morning and evening diary) and mean daily frequency of mild, moderate, and severe HFs (morning and evening diary) as well as the change from baseline values will be analyzed using descriptive statistics by study treatment and week. The change from baseline over time by study treatment will be shown using line plots for means and 95% CI.

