4.6.3 Sleepiz One+

The analyses of sleep parameters derived from Sleepiz One + monitor will be presented for the SLAS.

The Sleepiz One+ monitor will be provided to participants at screening to continuously collect sleep data at home in addition to the nights of PSG assessment. Parameters derived from Sleepiz One+ to be analyzed will be:

- WASO (mins)
- SE (%)
- TST (hours)

Version 2.0 Page: 40 of 57

- SOL (mins)
- Wake up latency (mins)
- Awakening count
- Average awakening (per hour of sleep)
- Out of bed count
- Time in bed (hours)
- Respiratory irregularity index (RII) (per hour of sleep)
- Heart rate per minute (min, max, mean, median, 10th and 90th percentile)
- Breathing rate per minute (min, max, mean, median, 10th and 90th percentile)

See Section 6.2.2 for more details on the definition of each parameter.

The parameters listed above are provided by the vendor as nightly values. For the analysis, the weekly mean daily value will be used. The mean value for each study week will be calculated using available data during that week as:

For a particular parameter:

total value of the parameter during that week

total number of available days with data for that parameter during that week

Study week will be assigned using the definition in Section 4.1.2 using the start date of the recording as the date of observation. If the start time of the recording is on or before 11:00, then the date of recording – 1 will be used as the date of observation. The mean daily value can be derived if a value is provided for at least 4 out of 7 nights, otherwise the mean daily value will be set as missing. The baseline value will be calculated similarly using all available days during the 14 days prior to starting treatment. A minimum of 7 days should be available for the derivation of the baseline value.

In single cases of concern that data was not transmitted properly during the participant's Sleepiz One+ use at home, the device will be switched on at site for 24 hours (after the participant returns the device) to transmit potentially stored data. Data recorded during this time will not be analyzed or listed. Therefore, data on or after last PSG assessment date + 1 or last treatment date + 1 or EoT visit date (whichever is the latest) will be excluded from the analysis.

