6.4.2 Temporary treatment interruption

Temporary treatment interruption is defined as

- Treatment taken < 80% during day 1 to the last PSG night at week 4 (inclusive) OR treatment taken on < 5 days during the last 7 days up to the last PSG night at week 4 (inclusive) for week 4.
- Treatment taken < 80% during day 1 to the last PSG night at week 12 (inclusive) OR treatment taken on < 5 days during the last 7 days up to the last PSG night at week 12 (inclusive) for week 12.

If the week 4 PSG assessment is missing, day 30 will be used instead of the last PSG night in the definition of treatment interruption for week 4 only for participants who have not prematurely discontinue treatment prior to day 30. Similarly for week 12, day 86 will be used only for participants who have not prematurely discontinue treatment prior to day 86.

The criterion for treatment taken on 5/7 days during the corresponding week prior to and including the last PSG night, as defined above, is met, if treatment has been taken for less than 5 days (i.e., at least 3 missed intakes). To calculate the number of days per week with treatment intake, a day where at least one capsule was taken, will be considered as a day with treatment intake.

To identify whether < 80% treatment was taken, compliance up to and including the last PSG night at week 4 will be calculated as

100 * Number of capsules taken up to and including the last PSG night at week 4 / (2 * study duration up to and including the last PSG night at week 4)

Compliance up to and including the last PSG night at week 12 will be calculated as

100 * Number of capsules taken up to and including the last PSG night at week 12 / (2 * study duration up to and including the last PSG night at week 12)

Study duration up to and including the last PSG night at week 4 and week 12 is derived as the number of days from the day of first study intervention intake up to and including the last PSG night at week 4 and week 12 respectively. The number of capsules taken up to and including the last PSG night at week 4 and week 12 will be calculated based on the ePRO instrument 'Study medication intake documentation'. If the 'Study medication intake documentation' on the second PSG night at week 12/EoT is missing but the last treatment intake on the eCRF 'Study intervention' pages indicate that the participant took treatment on

Version 2.0 Page: 54 of 57

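### With a first Week 12 PSG night on day 85 or 86, the hot-flash, sleep-diary and Sleepiz weekly means for Week 12 cannot be derived, and the hot-flash/WASO pairing drops those visits

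*SAP*

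**What the plan says.** **Study weeks.** SAP 4.1.2 explains its week formula by saying "This would therefore calculate study day 1 to 7 as study week 0" and that "day 29 and day 85 with a plus 7-day visit window are specified for week 4 and 12 respectively". Week 12 is then days 85–91.

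**Timing of the last visit.** The protocol's Schedule of Activities puts T3/EoT at day 85 with a window of +7 days, and its footnote b places the EoT assessments on the morning following PSG night 2. SAP 6.4.2 uses day 86 as the stand-in for a missing last PSG night: "Similarly for week 12, day 86 will be used only for participants who have not prematurely discontinue treatment prior to day 86". The on-schedule nights are therefore days 85 and 86, and EoT is the morning of day 87.

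**End of collection.** Protocol 8.2.2.2 has the HFDD completed "on the handheld device from visit SCR-1 until EoT as reflected in the SoA", and 8.2.2.1 says the same of the Sleep Diary. The handheld and the Sleepiz device are collected at EoT. SAP 4.6.3 drops Sleepiz data from the latest of three dates: the day after the last PSG, the day after the last treatment, and the EoT visit. On schedule all three are day 87.

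**Minimum data.** HFDD (SAP 4.4.3): "A minimum of 4 days should be available within a study week for the derivation of mean daily frequency". Sleep Diary (4.4.2): "The mean daily value can be derived if a value is provided for at least 4 out of 7 days with morning data". Sleepiz (4.6.3): "The mean daily value can be derived if a value is provided for at least 4 out of 7 nights". Below that the weekly value is missing. None of the three sections makes an exception for a last week cut short by EoT.

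**Pairing with PSG.** SAP 4.4.3: "The mean daily HFs for the same week the week 4 and week 12/EoT PSG assessments fall in will be plotted against each other".

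**The concern.** Week 12 begins on the day the Week 12 visit is due, and the visit ends collection. A participant who completes every entry and has her PSG on the nominal nights therefore has too few Week 12 days, and data already collected are discarded by the derivation. This affects the Week 12 points of the hot-flash, sleep-diary and home-monitor curves, and the Week 12 pairs for the exploratory objective on hot flashes and PSG-measured sleep. The Sleep Diary and Sleepiz each have a separate summary of values from the PSG nights. The HFDD has none, so for hot flashes nothing replaces the lost value.

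**Working it through.** **1. Week formula.** The formula itself is not legible in the text reviewed. CEIL(day/7) − 1 is inferred from the SAP's statements: day 7 → 0, day 29 → 4, day 85 → 12, day 91 → 12, day 92 → 13. Table 4-5 provides a check, because it assigns a PROMIS assessment to the week holding most of its 7-day recall. An assessment on day 88 recalls days 81–87, with 4 days in Week 11 and 3 in Week 12, so it goes to Week 11. Day 89 recalls days 82–88, with 3 and 4, so it goes to Week 12. That is the table's own boundary (82–88, 89–95), and the formula reproduces its other rows from Week 0 on.

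**2. Days available.** Let f be the first PSG night, taken over the allowed window, days 85–92. The last diary day or night collected is f + 1. SAP 4.4.2 and 4.4.3 use the diary day (the evening and the following morning) as the observation date.

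- Week 12 days: min(91, f + 1) − 84.
- If the combined day-and-night hot-flash week is shifted by one day (86–92): min(92, f + 1) − 85. SAP 4.4.3 states that shift for week 0 only (diary days 2–8), so carrying it forward is an assumption.

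| First night f | Last night | EoT | Week 12 days (need 4) | If shift carried forward | Study week of the two nights |
|---|---|---|---|---|---|
| 85 | 86 | 87 | 2, missing | 1, missing | 12, 12 |
| 86 | 87 | 88 | 3, missing | 2, missing | 12, 12 |
| 87 | 88 | 89 | 4, no slack | 3, missing | 12, 12 |
| 88 | 89 | 90 | 5 | 4 | 12, 12 |
| 89 | 90 | 91 | 6 | 5 | 12, 12 |
| 90 | 91 | 92 | 7 | 6 | 12, 12 |
| 91 | 92 | 93 | 7 | 7 | 12, 13 |
| 92 | 93 | 94 | 7 | 7 | 13, 13 |

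All counts assume complete entries. If morning entries were counted by calendar day instead, which is not the SAP's rule, f = 85 would give 3 days and still fail, while f = 86 would give 4.

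**3. Pairing.** The hot-flash mean comes from the study week in which the PSG falls.

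- f = 85 or 86: Week 12 mean missing, pair lost.
- f = 92: both nights are in week 13, which holds diary days 92 and 93 only. That is 2 days, so the pair is lost.
- f = 91: the nights fall in weeks 12 and 13, and no rule says which to use.
- Week 4: the mean is not lost, because collection continues (7 of 7 days).

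**4. Share affected.** The documents give no distribution of visit days. If every start is on day 85 or 86, 100% lack a Week 12 mean; if none is, 0%; if starts are spread evenly, 2/8 = 25% for night measures. For combined hot flashes with the shift carried forward, the even-spread figure is 3/8 = 37.5%.

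**5. The alternative window.** The 7 days ending on the last PSG night are f − 5 to f + 1. For f = 85 these are days 80–86, giving 7 days instead of 2, and the window is complete for every f. Its overlap with Week 11 (days 78–84) is max(0, 90 − f): 5 days for f = 85, 4 for 86, 3 for 87, and none from 90 on.

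**The case against.** The strongest reply is about scope. A start on any of days 85–92 is within the window, and the protocol allows treatment to run up to a week longer for sleep-laboratory scheduling. A reader might infer that every participant seen on time loses her Week 12 value, or that the Week 12 points come only from late attenders. The documents support neither: only day 85 and 86 starts fail for night measures, and those starting on days 87–92 are not late. Nor can one say that most participants are affected, since visit days are not given.

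A reader might also infer that a separate Week 12 hot-flash/WASO comparison collapses. SAP 4.4.3 pools the visits in one scatterplot and prints the number of observations, so the loss is of points in a pooled plot, and it is visible. It is not confined to early starts either, since a day 92 start loses its pair too.

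At Week 4, PSG nights 29–30 would be paired with a mean over days 29–35, 5 of which follow the PSG. It is tempting to call that an error, but the objective is to explore a relationship, no temporal order is claimed, and with nights 34–35 no day follows. It is a reason for one consistent anchor, not a fault of its own.

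Finally, the analyses are descriptive, the rule is the same in both arms, and weekly means through Week 11 are intact. All of this limits the consequence. It does not supply the missing exception for a first PSG night on day 85 or 86.

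**Conclusion.** The point holds in limited form. By the SAP's own rules, a participant with complete entries and a first Week 12 PSG night on day 85 or 86 has 2 or 3 qualifying days against a minimum of 4, and so no Week 12 weekly mean for the HFDD, Sleep Diary or Sleepiz. A day 87 start qualifies only if no entry is missed, and would fail for combined hot flashes if the one-day shift applies beyond week 0. The hot-flash/WASO pairing loses the Week 12 pair for starts on days 85, 86 and 92, and is undefined for day 91.

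This rests on the inferred week formula, which Table 4-5 confirms, and on the +7 window applying to the first PSG night. The proportion affected is unknown.

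The affected endpoints are exploratory or other. Primary and secondary PSG results are untouched, and the Sleep Diary and Sleepiz keep their PSG-night summaries. It is worth correcting because the data exist and the remedy is cheap, not because a main conclusion is at risk.

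**What to change.** **SAP 4.4.3, scatterplots and correlations.** Pair each Week 4 and Week 12/EoT PSG value with the hot-flash mean over the 7 diary days ending on that visit's last PSG night, with at least 4 available. SAP 6.4.2 already uses this 7-day window for treatment interruption. It removes the day 85, 86, 91 and 92 problems together.

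**SAP 4.4.2, 4.4.3 and 4.6.3, weekly curves.** Keep calendar study weeks, including Week 4, where nothing is missing. Use the PSG-anchored window only for the final Week 12/EoT point, and label it as the last 7 days on treatment. Where the Week 12 PSG is missing, 6.4.2 already provides day 86 as the anchor for participants still on treatment. State whether the one-day shift for combined hot flashes applies after week 0.

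**Cost.** SAP wording and one derivation; no new data. The drawback is overlap: on schedule, 5 of the 7 days (80–84) also enter the Week 11 point, so that curve's last two points are not independent. A footnote should say so.

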5.1 Inclusion Criteria

Participants are eligible to be included in the study only if all the following criteria apply:

Age

1. Females aged 40 to 65 years, inclusive, at signing of informed consent.

21 SEP 2023 Page: 25 of 73

Type of Participant and Disease Characteristics

2. Being in the post-menopausal period, defined as: serum FSH levels >40 mIU/mL and a serum estradiol concentration of <30 pg/mL at screening,

AND

Hysterectomy performed at least 6 weeks prior to screening.

3. Experiencing VMS associated with menopause, defined as:

Participant has completed HFDD for at least 11 days during the 2 weeks prior to the respective eligibility check, and during this period participant has recorded a weekly average of at least 20 moderate or severe HF (including night-time HF).

- 4. The participant's self-reported sleep history includes ongoing sleep disturbances associated with menopause characterized by waking up at night and/or poor quality of sleep.
- 5. The participant's self-reported ongoing sleep disturbances cause distress or impairment in social, occupational, or other important areas of functioning.
- 6. WASO of 30 minutes or more (mean of 2 screening PSGs with neither of the 2 nights <20 min).
- 7. The participant's self-reported time in bed between 6 and 9 hours.
- 8. The participant's self-reported bedtime is usually between 21.00 and 24.00 hours and it does not vary by more than ± 2 hours.
- 9. Negative urine pregnancy test at screening.
- 10. BMI between 18 and 38 kg/m² at screening.

Informed Consent

11. Capable of giving signed informed consent as described in Section 10.1.3 which includes compliance with the requirements and restrictions listed in the ICF and in this protocol.

Additional criteria

- 12. Normal breast cancer screening result available prior to start of treatment in line with the method and frequency recommended in the respective country. The time elapsed since the last screening examination should be sufficiently short that no further routine screening examination needs to be scheduled during the course of the study. ²
- 13. In individuals with a cervix: normal cervical cancer screening result available prior to start of treatment in line with the method and frequency recommended in the respective country. The time elapsed since the last screening examination should be sufficiently short that no further routine screening examination needs to be scheduled during the course of the study.

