6.5 Study Intervention Compliance

When participants self-administer study intervention(s) at home, compliance with study intervention will be assessed by site/study personnel/staff at each visit. Compliance will be assessed by review of daily diary entries and confirmatory capsule counts during the site visits and documented in the source documents and relevant form by site. Deviation(s) from the prescribed dosage regimen should be recorded.

A record of the number of capsules dispensed to and administered by each participant must be maintained and reconciled with study intervention and compliance records. An adequate record of receipt, distribution, and return/destruction of all study intervention must be captured on the dispensing log and/or in the IRT. If the participant is unable to continue taking the study intervention as required, she should contact the study site.

Study intervention capsules not returned will be considered to have been taken unless otherwise specified. At the end of the study, any remaining capsules will be collected and returned to the Sponsor, destruction depot or destroyed at the site. Any discrepancies between the returned and expected returned study interventions should be explained.

Study medication intake documenting

Participants will document the number of study medication capsules taken, together with the HFDD evening diary once daily at bedtime using the 'Study medication intake documentation' on the electronic handheld device during the treatment period as indicated in the SoA.

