In addition to the technical support by the study site staff, a 24-hour help desk by the ePRO provider will be available during the entire study duration to respond urgent technical questions.

Measures to further prevent missing participants' handheld device entries

In case one entry on the HFDD, the SD or the study medication intake documentation was missed (for HFDD morning diaries and SD in case this was not completed when getting up in the morning; for HFDD evening diaries, and the study medication intake documentation in case this was not completed in the evening when going to bed), retrospective data entry is possible for a pre-defined period of time (provided separately).

When the study site becomes aware of missing participant handheld device entries, the study site staff will contact the participant who have missed a defined number of consecutive entries (provided separately) immediately, and ask for reasons for failure in data entry and transfer. The study site staff will remind the participants the importance of the twice daily eDiary entry.

Further to the automatic continuous checking of completeness of the participant handheld device entries, at all the study visits following SCR-2, the participant handheld device entries will be checked, and the checks documented by the study site personnel for completeness.

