4.1.1.3 Electronic Patient Reported Outcomes (ePROs)

There are two types of missing data for ePRO measures: missing data at the 'form' level and missing data at the 'item' level.

Form level missing refers to a participant missing an entire PRO assessment for a given time point (e.g., a given day (i.e., morning and evening) for the HFDD and a given week for the PROMIS SD SF 8b). In general, form level data may be missing due to participant's early withdrawal from the study, inability to evaluate an endpoint at a particular time point, or noncompliance.

By design of the eDiary, there will be no item level missing data for the respective ePRO questionnaires because the participants have to select an answer for an item in order to move on to the next item on the eDiary/electronic handheld device, with the exception for the eC-SSRS where the form can be submitted even if incomplete.

No imputation of missing assessments will be performed for any ePRO measures.

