4.4.3 Hot Flash Daily Diary (HFDD)

- Frequency of HFs as measured by HFDD over time
- Change from baseline in proportion of days with participants rating "quite a bit" or "very much" sleep disturbance due to HF as measured by HFDD over time

Participants' assessments of HFs will be recorded electronically twice daily using the sponsor developed HFDD. The HFDD is completed in the morning after waking up (morning diary) and each evening at bedtime (evening diary) on the hand-held device. The HFDD assess the number of mild, moderate, and severe HFs experienced during the day (evening diary) and during the night (morning diary). Therefore, a diary day consists of the evening entry and the morning entry of the subsequent day.

Version 2.0 Page: 31 of 57

Mild HFs are defined as a "sensation of heat without sweating", moderate HFs are defined as a "sensation of heat with sweating, but able to continue activity", and severe HFs are defined as a "sensation of heat with sweating, causing cessation (stopping) of activity".

The following daily HF assessments will be aggregated to a mean daily frequency for each study week:

- moderate to severe nighttime HFs (morning diary)
- mild, moderate, and severe nighttime HFs (morning diary)
- moderate to severe HFs (morning and evening diary)
- mild, moderate, and severe HFs (morning and evening diary)

The mean daily frequency of moderate to severe nighttime HFs for a study week will be calculated as

total number of nighttime moderate to severe HFs during that week total number of available days with morning data during that week

The calculation of mild, moderate, and severe nighttime HFs, moderate to severe HFs and mild, moderate, and severe HFs will be calculated similarly to the above.

Study week will be assigned using the definition in Section 4.1.2. using the diary day as the date of observation. Data entered on the morning after the start date of treatment / randomization date will not be used in the calculation of baseline value but will be considered post-baseline for nighttime HFs. For the mean daily frequency using both the morning and evening diary (i.e., moderate to severe HFs and mild, moderate, and severe HFs), diary day 2 - 8 will be used for week 0.

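### SAP 4.4.3 counts a half-observed diary day as a full day for the two combined hot-flash frequencies, so these exploratory means are understated when a missed entry would have held a counted hot flash

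*SAP*

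**What the plan says.** SAP 4.4.3 treats a diary day as two halves: the evening entry, which records daytime HFs, and the entry of the following morning, which records night-time HFs. It defines four weekly measures. Two use the morning diary only. The other two (moderate to severe HFs; mild, moderate and severe HFs) use both diaries.

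The formula is written out only for night-time moderate to severe HFs: the week's total over the number of days with morning data. For the others the SAP says that "moderate to severe HFs and mild, moderate, and severe HFs will be calculated similarly to the above". It then defines an available day. For the night-time measures the morning entry must exist. For the combined measures a day counts "if either evening entry or morning entry (of the subsequent day) is available when both evening and morning diaries are used". At least 4 available days are needed in a study week, and at least 7 in the 14 days before treatment for the baseline value.

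On missing data, SAP 4.1.1.3 states that "No imputation of missing assessments will be performed for any ePRO measures", and SAP 4.4 repeats that exploratory endpoints are not imputed. The example of form-level missingness in 4.1.1.3 is "a given day (i.e., morning and evening) for the HFDD", that is, a whole day. Protocol 8.2.2, however, foresees the loss of a single entry and allows late entry for a limited time: "In case one entry on the HFDD, the SD or the study medication intake documentation was missed".

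**The concern.** For the night-time measures, numerator and denominator match: morning counts over days with a morning entry. For the combined measures they do not. A day with only an evening entry contributes its daytime HFs and a full day, while its night-time HFs are left out as if they were zero. The reverse holds for a day with only a morning entry. The weekly minimum can be met by half-days alone.

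At stake are the only HF frequencies that 4.4.3 summarises by treatment and week, with change from baseline and line plots. These measures also feed half of the HF-WASO scatterplots: 4 measures × 3 scales (actual, change, percent change) = 12 plots, of which 2 × 3 = 6 use the combined measures.

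**Working it through.** The documents state no figure for this derivation, so there is none to reproduce. They also give no miss rates and no day/night split of HFs; all such values below are assumptions. That a missed half counts as zero is inferred from the total-over-available-days formula and the no-imputation rule, because the combined formula is not written out.

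**Expected value under the rule.** Let D and N be the true daytime and night-time HFs per day, e and m the evening and morning miss rates, and p the probability that both entries of a day are missed. Then

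expected mean = [(1 − e)·D + (1 − m)·N] / (1 − p), against a true D + N.

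**Equal miss rates q.**
- Independent misses: p = q², so the ratio to truth is (1 − q)/(1 − q²) = 1/(1 + q). For q = 5%, 10%, 20% this is 0.952, 0.909, 0.833: understated by 4.8%, 9.1%, 16.7%.
- Correlation 0.5: p = q² + 0.5·q(1 − q). The ratios are 0.95/0.97375 = 0.976, 0.90/0.945 = 0.952 and 0.80/0.88 = 0.909: understated by 2.4%, 4.8%, 9.1%.
- Whole-day gaps only: p = q and the ratio is 1, so there is no bias.

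A simulation of 400,000 participant-weeks with Poisson counts, independent misses and the 4-day minimum agrees: against a true 2.857 per day (20 per week, the entry threshold), the rule gives 2.721, 2.599 and 2.381.

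**One participant, one missed evening entry, 3 daytime + 2 night-time HFs per day (true 5.0).**
- 7 available days: (7×5 − 3)/7 = 4.57, which is 8.6% low.
- 4 available days: (4×5 − 3)/4 = 4.25, which is 15% low.
- If the missed half held no counted HF, the value is unchanged.

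**Change from baseline, true 5.0 to 2.5 = −2.50, independent misses.**
- Constant 10%: 2.5/1.10 − 5.0/1.10 = −2.27.
- Misses rise from 5% to 20%: 2.5/1.20 − 5.0/1.05 = −2.68.
- Misses fall from 20% to 5%: 2.5/1.05 − 5.0/1.20 = −1.79.

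Applying the same rule at baseline therefore does not cancel the error, and its direction is not fixed.

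**Difference between arms, same missingness in both (5% evening, 20% morning, independent; 1 − p = 0.99).**
- Same day:night ratio, 3+2 against 1.5+1: (2.85 + 1.60)/0.99 = 4.495 and (1.425 + 0.80)/0.99 = 2.247. The difference is 2.247, down 10.1% from 2.50, and each mean is also down 10.1%.
- Different ratio, 3+2 against 2+0.5: 4.495 and (1.90 + 0.40)/0.99 = 2.323. The difference is 2.172, down 13.1%, while the means are down 10.1% and 7.1%.
- Same true total, different ratio, 3+2 against 4+1: 4.49 and (3.80 + 0.80)/0.99 = 4.65, an apparent difference of about 0.15 per day where none exists.

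So, with identical missingness in the arms, the difference shrinks in proportion to the means if either the morning and evening rates are equal or the arms share the same day:night ratio. Otherwise it can be distorted.

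**Separate denominators.** In the simulation above, the daytime mean over evening entries plus the night-time mean over morning entries returns 2.857, 2.859 and 2.858 against the true 2.857.

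**The case against.** The best defence is that the effect is small in practice and touches nothing that matters for the trial's conclusion. Protocol 8.2.2 provides alarms, continuous completeness checks, site contact and retrospective entry, all aimed at these gaps. Inclusion criterion 3 also selects for diary compliance: "Participant has completed HFDD for at least 11 days during the 2 weeks prior to the respective eligibility check". No hypothesis is tested, and the apparent difference of 0.15 HF per day shown above needs arms with equal totals but different day/night splits. If the standard deviation were 1.5 to 3 HF per day (assumed), a 95% interval with 35 per arm would have a half-width of roughly 0.7 to 1.4, far larger than that.

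Most of this stands, and it is why the point is minor. It limits the size of the error but does not correct the formula. The entry criterion does not say whether a completed day needs both entries, and it does not cover the weeks after baseline.

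It could also be argued that the either-entry rule saves data. It does, but separate denominators also use every entry received, at little loss.

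A reader might infer more than the documents support:
- That the rule favours one arm. Nothing is known about misses by arm or by time of day, so no direction can be claimed.
- That the between-arm difference keeps its proportion only when morning and evening miss rates are equal. The 3+2 against 1.5+1 example shows otherwise.
- That the error reaches the primary model through the HF stratum. SAP 4.1.2 takes that value from the handheld device, not from this derivation.

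**Conclusion.** The concern holds, as a minor defect confined to exploratory measures. As written, the rule gives a half-observed day full weight in the denominator, and no other section of the SAP corrects for it. How much the means are understated depends wholly on how often single entries are missed, which the documents do not say; at the assumed rates of 5% to 20% the range is 2.4% to 16.7%, the lower values applying if misses cluster within days.

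Affected: the two combined HF frequencies, their change from baseline, their line plots, and the matching 6 scatterplots with their correlation coefficients. Not affected: WASO and the other secondary endpoints, the night-time HF measures, and the stratum used in the mixed model and the subgroup summaries. The documents do not support any claim that the primary result or the trial's conclusion is at risk.

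**What to change.** Write the formula for the combined measures out in SAP 4.4.3 as

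(daytime HFs / days with an evening entry) + (night-time HFs / days with a morning entry),

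with at least 4 entries of each kind in a study week and at least 7 of each kind in the 14-day baseline window.

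The cost is SAP wording and minor programming; no new data are needed. Some values become non-derivable. With independent misses, the chance of at least 4 of 7 entries of one kind is 0.9973 at a 10% miss rate and 0.9667 at 20%. Both kinds are needed, so 1 − 0.9973² = 0.5% and 1 − 0.9667² = 6.6% of participant-weeks are lost (5.8% at 20% if misses correlate at 0.5). At baseline, at least 7 of 14 of each kind fails for fewer than 0.01% of participants at 10% and about 0.5% at 20%.
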